#### 9.1.3 Other efficacy endpoints

To compare of sotagliflozin 400 mg and 200 mg versus placebo, respectively, in terms of:

- Change from Baseline in SBP at Weeks 26 and 52 for patients with Baseline SBP  $\geq 130$  mmHg
- Change from Baseline in SBP at Weeks 26 and 52 for all patients
- Change from Baseline in HbA1c at Week 52
- Change from Baseline in FPG at Week 52
- Change from Baseline in body weight at Week 52
- Change from Baseline in eGFR.

- Change from Baseline to Week 26 in:
  - Cystatin C
  - UGE
  - UGCR
  - Fructosamine
  - NT-proBNP
- Proportion of patients with progression to end stage renal disease (ESRD) (dialysis or transplant) at Week 4 or any time later during the trial
- Proportion of patients with >50% decline in eGFR from Baseline to Week 26 and Week 52
- Proportion of patients with progression from normal to microalbuminuria or from microalbuminuria to macroalbuminuria from Baseline to Week 26 and Week 52
- Proportion of patients with improvement from microalbuminuria to normal or from macroalbuminuria to microalbuminuria from Baseline to Week 26 and Week 52
- Change from Baseline to Week 12 in SBP for patients with baseline SBP <130 mmHg
- Change from Baseline to Week 12 in DBP for all patients and the subset of patients with baseline DBP  $\geq$ 80 mmHg
- Proportion of patients requiring rescue for hyperglycemia during 26-week double-blind period.

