2.3.1.1 Intent-to-treat population

Efficacy analyses will be based on the ITT population, defined as all randomized patients, irrespective of compliance with the study protocol and procedures. Patients will be analyzed for efficacy according to the treatment group to which they are randomized.

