2.4.4 Analyses of efficacy endpoints

Efficacy analyses will be performed on the ITT population using the efficacy assessments collected during the study, including those obtained after IMP discontinuation or introduction of rescue therapy, unless otherwise specified.

Statistical testing will be performed for primary endpoint and secondary endpoints at Week 26 (with the exception of Week 12 for SBP). All efficacy endpoints after Week 26 will only be summarized by descriptive statistics without formal statistical testing.

Missing data for efficacy analyses is identified through steps described in [Section 2.5.4](#).

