2.4.4.3 Analyses of other efficacy endpoints

The analysis of other endpoints (see [Section 2.1.3](#)) will be descriptive with no formal testing. Summary statistics at scheduled visits based on observed value will be provided by each treatment group. Graphical presentations will also be used to illustrate trends over time as appropriate.

The number (%) of patients who used rescue therapy will be provided by treatment group during the 26-week core (see [Section 2.5.4](#)) and the 52-week entire double-blind treatment periods. A KM curve for the time to first rescue therapy will be presented during the 26-week core treatment period and 52-week entire treatment period (see [Section 2.5.4](#)). The list of patients who used rescue therapy will also be provided.

ESRD is defined as: (1) dialysis that persists for a duration of \geq 90 days, or positively adjudicated as ESRD if dialysis $<$ 90 days; (2) eGFR $<$ 15 ml/min/1.73 m² sustained for at least 30 days or positively adjudicated as chronic; or (3) renal transplant. The number (%) of patients with progression to ESRD at Week 4 or any time later during the study will be summarized. The same analysis will be provided during the period from the first administration of double-blind IMP (or the date of randomization if not exposed) to Week 4 (exclusive). A KM plot will be provided for time to first occurrence of ESRD up to Week 26 and the end of study respectively (see [Section 2.5.4](#)).

The number (%) of patients with >50% decline in eGFR from baseline at each scheduled visit (including Week 26 and Week 52) will be presented. The same analysis will be presented from Week 4 at each scheduled visit afterwards (including Week 26 and Week 52). A KM plot will be provided for time to first occurrence of >50% decline in eGFR from baseline up to Week 26 and the end of study respectively (see [Section 2.5.4](#)).

The number (%) of patients with UACR progression from baseline to Week 26 and Week 52, (ie, from normal to microalbuminuria or from microalbuminuria to macroalbuminuria) will be provided by treatment group respectively. A KM plot will be provided for time to UACR progression up to Week 26 and the end of study respectively (see [Section 2.5.4](#)). Similarly, the number (%) of patients with UACR improvement from baseline to Week 26 and Week 52 (from microalbuminuria to normal or from macroalbuminuria to microalbuminuria) will be provided, as well as the KM plot if appropriate.

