As specified in the study protocol, laboratory data from scheduled visits are reported by central laboratories. The local results will not be used in the efficacy analyses or in the definition of baseline for both safety and efficacy analyses. In the safety analyses, for parameters with PCSA defined based on normal range, local results will be used in the PCSA summary if they are accompanied by a local laboratory normal range. For parameters with PCSA not defined based on normal range, local results will be used in the PCSA summary as appropriate.

When a patient has more than 1 measurement from the central laboratory for the same laboratory parameter on the same date, the average of the measurements will be used. For the same laboratory parameter, if a patient has more than 1 measurement on different dates for the same scheduled visit, the value closest to the date of the visit will be used for the scheduled visit. When the values for the same scheduled visit are equidistant, the last value should be used for the scheduled visit. Similar rules will be applicable to a patient who has more than 1 set of measurements for the same vital sign parameter (ie, SBP, DBP, or HR) on the same date.

26-week double blind core treatment period

The 26-week double-blind core treatment period is the time from first administration of double-blind IMP to the last administration of double-blind IMP on or before Visit 11 (Week 26) (or Day 182 if Visit 11 (Week 26) date is missing). This is for defining EOT status at Week 26 and analyzing selected efficacy parameters (eg, rescued patients) during the core treatment period.

TEAE period for the 26-week double blind core treatment period

The TEAE period for the 26-week double-blind core treatment period is (1) the time from the first administration of the double-blind IMP up to 15 days (1 day for hypoglycemia) after the last administration of IMP if the patient discontinued treatment on or before Visit 11 (or Day 182 if Visit 11 date is missing), or (2) the time from the first administration of the double-blind IMP to the administration at Visit 11 (Week 26) (or Day 182 if Visit 11 (Week 26) date is missing) if the patient remained treated beyond Visit 11 (Week 26). This is for the purpose of safety analyses during the core treatment period.

26-week core study period

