The 26-week core study period is the time from first administration of double-blind IMP to Visit 11 (Week 26) (or Day 182 if Visit 11 (Week 26) date is missing) or the end of TEAE period for the 26-week double-blind core treatment period (as defined above) whichever is later. This is for defining EOS status at Week 26.

Time to event analysis

For time to event analysis/KM plot, time to event (eg, treatment discontinuation, rescue therapy, hypoglycemia, ESRD, etc) is defined as the number of days from the date of the first administration of double-blind IMP (or the date of randomization if not exposed) to the start date of the first occurrence of the event during the respective analysis period.

Patients who did not experience any event during the respective analysis period are considered censored observations. The censoring rules are defined below.

Time to event	Censoring date at Week 26 (1st step analysis)	Censoring date at EOT/EOS (2nd step analysis)
Treatment discontinuation due to any reason	Not applicable	EOT
Treatment discontinuation due to AE	Not applicable	EOT
Time to rescue	min (EOT, Date of W26 visit)	EOT
Time to severe or documented hypoglycemia	See Section 3	Min (EOT+1, EOS)
Time to ESRD	min (EOS, Date of W26/re-allocated W26 eGFR value)	EOS
Time to eGFR decrease	min (EOS, Date of W26/re-allocated W26 eGFR value)	EOS
Time to UACR progression/improvement	min (EOS, Date of W26/re-allocated W26 UACR value)	EOS

Note: (1) Day 182 will be used if Date of Week 26 visit (or date of W26/re-allocated W26) is not available.
(2) Date of EOS will be used if date of EOT is not available; Last contact date will be used if date of EOS is not available.

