Week 26		at screening)	/ SBP at screening): excluding patients with baseline HbA1c values <6.5% (for <6.5% responders) or <7% (for <7% responders) respectively		(<6.5%, <7%). By-visit frequency summary and graphs of HbA1c responders (<6.5%, <7%) excluding patients with baseline HbA1c values <6.5% or <7% respectively. See Section 1.6 for additional planned analyses.
Other endpoints					
SBP (for patients with baseline SBP <130 mmHg), DBP (for all patients and patients with baseline ≥80 mmHg), UACR, UGE, and UGCR, eGFR: change from baseline	ITT	Summary statistics for observed values and changes from baseline by visit.	No	No	Graphical presentations for mean changes from baseline (±SE) and mean values (±SE) by visit as appropriate.
Proportion of patients with >50% decline in eGFR; with progression to end-stage renal disease, with progression/improvement of UACR categories,	ITT	By-visit frequency summary	No	No	By-visit graphical presentation as appropriate
Proportion of patients requiring rescue for hyperglycemia		Summary statistics	No	No	KM plot; List of patients rescued

Statistical Analysis Plan

Version: Final 3.0

Lexicon Pharmaceuticals Protocol No. EFC15166

Date of Issue: 21 November 2019

Covance Study ID: 000000155203

Endpoint	Analysis population	Primary analysis	Supportive analysis	Subgroup analysis	Other analyses
hypoglycemia	Safety	Follow safety guidelines Number (%) of patients with any hypoglycemia, severe hypoglycemia, documented symptomatic hypoglycemia during TEAE period, and incidence rates in 100 patient-years.		Severe hypoglycemia or documented symptomatic hypoglycemia by subgroups: race, age, gender	KM plot time to first event of severe hypoglycemia or documented symptomatic hypoglycemia Documented symptomatic hypoglycemia maybe presented by <54 mg/dL (3.0 mmol/L) as appropriate.
Adverse Events	Safety	Follow safety guidelines	No	Common TEAEs by subgroups: race, age, gender, baseline SBP	
Clinical laboratory data	Safety	Follow safety guidelines	Descriptive	No	No
Vital signs	Safety	Follow safety guidelines	Descriptive	No	No
ECG, Physical examination	Safety	Follow safety guidelines	Frequency summary	No	No

Statistical Analysis Plan

Version: Final 3.0
Lexicon Pharmaceuticals Protocol No. EFC15166

Date of Issue: 21 November 2019
Covance Study ID: 000000155203

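### The rescue count and the time-to-rescue curve end at the last IMP dose, so the reported n (%) understates the protocol's 26-week proportion if any rescue starts after IMP is stopped (minor; descriptive endpoint)

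*SAP*

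**What the plan says.** Protocol 9.1.3 lists the endpoint as "Proportion of patients requiring rescue for hyperglycemia during 26-week double-blind period". Protocol 6.1.2 heads that period Day 1 to Week 26, with no cut at the last dose.

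SAP 2.4.4.3 turns this into a table: "The number (%) of patients who used rescue therapy will be provided by treatment group during the 26-week core" period, with a pointer to 2.5.4, and likewise for the 52-week treatment period. SAP 2.5.4 runs the core treatment period from the first dose "to the last administration of double-blind IMP on or before Visit 11 (Week 26"), using Day 182 if the visit date is missing. It says the window serves to define treatment status at Week 26 and for "analyzing selected efficacy parameters (eg, rescued patients) during the core treatment period". In the censoring table of the same section, time to rescue is censored at "min (EOT, Date of W26 visit") for the 26-week curve and at EOT for the 52-week curve.

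On population, SAP 2.3.1.1 states: "Efficacy analyses will be based on the ITT population, defined as all randomized patients, irrespective of compliance with the study protocol and procedures". SAP 2.4.4 adds: "Efficacy analyses will be performed on the ITT population using the efficacy assessments collected during the study, including those obtained after IMP discontinuation", or after rescue; the same sentence allows exceptions specified elsewhere. In SAP Appendix D, the row "Proportion of patients requiring rescue for hyperglycemia" has an empty analysis-population cell.

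**The concern.** A patient who stops IMP at Week 10 and starts rescue at Week 14 falls outside the window and is tabulated as not rescued. The same patient's Week 26 HbA1c, measured under the rescue drug, does enter the primary analysis. If the patient is a retrieved dropout, it also feeds the imputation of others in that arm who stopped IMP (SAP 2.4.4.1). A reader of the treatment-policy HbA1c result wants to know how much rescue lies behind it in each arm, and the table would omit this part.

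The omission need not be equal across arms. It grows with the share of patients who stop IMP, and the protocol has creatinine-driven stopping rules (8.1.1, 10.3.3) that could operate differently by arm. A difference in stopping could then look like a difference in rescue.

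**Working it through.** **Is later rescue added back anywhere?** No section does so. SAP 2.1.3 identifies rescue from the reason ticked on the e-CRF medication page, with no on-IMP condition. Protocol 10.3.4 keeps patients under study procedures after a permanent stop, and the visit lists in protocol 10.1.2.3 and 10.1.2.4 include rescue evaluation. The data should therefore exist, and the window alone excludes them. In the censoring table, ESRD, eGFR decrease and UACR change are followed to EOS; rescue is the only efficacy event cut at EOT. SAP 2.5.4 also defines a 26-week core study period that runs at least to Visit 11 whether or not IMP was stopped, but uses it only for end-of-study status.

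**Arm size.** The plan gives no figure for rescue. The only planning figure used here is 92 per group (protocol 11.1: SD 1.2%, difference 0.5%, two-sided 0.05). It reproduces: the t-test needs 91.4, rounded up to 92, with power 0.803 at 92.

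**Illustration (all rates are assumptions).** Take the 26 weeks as one time unit and let times to rescue and to IMP stop be independent and exponential. R is the 26-week rescue risk with nobody stopping, D the share stopping, r = −ln(1−R), d = −ln(1−D), and k the ratio of the off-IMP to the on-IMP rescue hazard.

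- Counted share = r/(r+d) × [1 − exp(−(r+d))]
- Full 26-week share = counted + ∫₀¹ d·exp(−(r+d)t)·[1 − exp(−k·r·(1−t))] dt

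Example with R = D = 20%: r = d = 0.2231, so counted = 0.5 × (1 − 0.64) = 18.0%. With k = 1 the full share is 20.0%. Missed: 2.0 points, or 0.020 × 92 = 1.8 patients.

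For R = 20%:

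| Stop IMP | Counted | Missed of 92, k = 0 | k = 1 | k = 2 |
|---|---|---|---|---|
| 5% | 19.5% | 0 | 0.4 | 0.8 |
| 10% | 19.0% | 0 | 0.9 | 1.7 |
| 20% | 18.0% | 0 | 1.8 | 3.4 |
| 30% | 16.9% | 0 | 2.8 | 5.2 |

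Across R of 10% to 30% the largest value is 7.4 patients (R = 30%, D = 30%, k = 2).

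**Two arms with the same R = 20%, stopping 10% versus 25%.** Counted: 0.2231/0.3285 × 0.28 = 19.0% and 0.2231/0.5108 × 0.40 = 17.5%. With k = 1 the full share is 20.0% in both arms, so about 1.5 points of apparent advantage is an artifact (0.8 at R = 10%, 2.3 at R = 30%). With k = 2 the full shares are 20.8% and 22.2%, so the order reverses.

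**Kaplan-Meier curve.** Censoring at EOT takes these patients out of the risk set; they are not treated as free of rescue. In this model stops are independent of rescue, so the curve would estimate R = 20% in both arms. What it relies on is that censoring at EOT is non-informative. It describes risk while on IMP, not the full 26-week proportion when k differs from 1.

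**The case against.** The SAP's general rule on post-discontinuation data yields to exceptions, and 2.5.4 is such an exception: it names rescued patients and is matched by the censoring rule. A reader might infer that the SAP breaks its own ITT rule. It does not.

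The protocol also gives an on-treatment reading some support. Rescue is to be reported throughout the treatment period (9.1.4.7), the investigator first checks that IMP is being given as planned, and a rescued patient continues IMP (8.2.1). Glucose-lowering drugs started after a stop may be replacement for the study drug rather than rescue; protocol 10.3.3 expects therapy to be adjusted when IMP is stopped. Later use is not hidden either: SAP 2.4.4.3 promises a list of rescued patients, and SAP 2.4.2 tabulates concomitant and post-treatment medication by arm, with antidiabetic drugs shown separately.

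These points stand. They make the window a defensible choice for an on-treatment question, but the SAP never states that question. A crude percentage of all randomized patients does not answer it well either, because it ignores the shorter time on IMP of those who stop. The medication tables do not yield a rescue percentage.

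**Conclusion.** The count and the curve stop at the last dose, while the protocol endpoint covers Day 1 to Week 26. On the ITT denominator, the n (%) is below the 26-week proportion whenever any rescue starts after a stop, and more so in an arm with more stops. That denominator is itself inferred from the general rule, since the Appendix D cell is blank.

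The size is illustrative: about 0 to 5 of 92 patients per arm in most scenarios, under assumed rates and independent exponential times. It is zero if no rescue follows a stop.

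Two stronger conclusions are tempting. One is that the endpoint will be biased in favor of sotagliflozin. The documents give no rescue rate, no discontinuation rate and no expected arm difference, so neither that direction nor its size can be asserted. The other is that the efficacy conclusion is compromised. The endpoint is descriptive and outside the testing hierarchy; no alpha, primary estimate or imputation rule depends on it. This is a minor point.

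**What to change.** In SAP 2.4.4.3, 2.5.4 and Appendix D:

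- State that the denominator is the ITT population.
- Add a count of patients with rescue from Day 1 to Visit 11 (Day 182 if the date is missing), regardless of IMP status. For the 52-week figure, count to Visit 13 (Day 364 if missing). Do not extend it to EOS: the rescue thresholds end at Week 52, and Visit 14 has no rescue evaluation, FPG or HbA1c.
- Add a time-to-rescue curve censored at the earlier of EOS and that visit date.
- Keep the existing on-IMP count beside the new one.
- Label the new count as added after the Week 26 top-line analysis, which SAP 1.6 says has already been conducted and reported.

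The cost is SAP wording, one table row per period and the matching curves, from data already collected. The downside is that some treatment counted after a stop may be replacement therapy; showing the on-IMP row next to it lets the reader separate the two.

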### **6.1.2 Double-blind Treatment Period (Day 1 to Week 26)**

Eligible patients will be randomized on Day 1 (Visit 3). In order to qualify for randomization, patients must also demonstrate compliance during the single-blind placebo Run-in Phase based upon tablet count ( $\geq 80\%$ ) and, as assessed, at the Investigator's discretion.

Randomization will be stratified by:

- HbA1c at Screening ( $\leq 8.5\%$  and  $> 8.5\%$ )
- SBP at Screening ( $< 130$  mmHg,  $\geq 130$  mmHg).

Following randomization, patients will be treated in a double-blind manner for 26 weeks. A total of 276 patients  $\geq 18$  years of age (or  $\geq$  legal age of the majority, whichever is greater) are planned to be randomly assigned 1:1:1 to the following treatment groups:

- Placebo, given as 2 placebo tablets (identical to sotagliflozin 200 mg in appearance), once daily
- Sotagliflozin 200 mg, given as 2 tablets: 1 sotagliflozin 200 mg tablet and 1 placebo tablet (identical to sotagliflozin 200 mg in appearance), once daily
- Sotagliflozin 400 mg, given as 2 sotagliflozin 200 mg tablets, once daily.

Fasting glucose (plasma or serum) and HbA1c results will be masked to study sites and patients after randomization until study end. To prevent partial unblinding, UGE and UGCR will be masked to study sites and patients, and the central laboratory urine dipstick will not include the measurement of urine glucose.

Quantitative urine glucose, albumin, calcium, and creatinine will be measured separately at selected on-site visits by the central laboratory.

All visits will be on-site visits.

If a patient discontinues treatment with investigational medicinal product (IMP) early during the Treatment Period, the patient will have a premature end of treatment (EOT) Visit and a Follow-up Visit, 4 weeks ( $\pm 5$  days) after the last dose of IMP. In addition, every effort will be made to have all patients return to the site at the time corresponding to their scheduled visits, particularly the Weeks 26 and 52 Visits.

If a patient does not agree to site visits, he/she will be contacted by telephone to inquire about their safety status, particularly at the time of the initially scheduled end of study.

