2.1.4 Safety endpoints

The safety analysis will be based on the reported adverse events, hypoglycemia, acute renal failure and other safety information, such as clinical laboratory data, vital signs, electrocardiogram (ECG), physical examination and marker of intestinal transit and absorption, markers of bone and calcium metabolism, etc.

Observation period

The observation period will be divided into 4 epochs:

- The **screening** epoch is defined as the time from the signed informed consent date up to the first administration of the double-blind IMP.
- The **treatment** epoch is defined as the time from the first administration of double-blind IMP to the last administration of double-blind IMP. This epoch includes the 26-week double-blind core treatment period and the 26-week double-blind extension treatment period. The 26-week core treatment period is the time from the first administration of double-blind IMP to the last administration of double-blind IMP on or before Visit 11 (Week 26) [or Day 182 if Visit 11 (Week 26) date is missing].
- The **residual treatment** epoch is defined as the time from the last administration of the IMP to the last administration of the IMP + 15 days (1 day for hypoglycemia).

The treatment-emergent adverse event (TEAE) period will include both **treatment** and **residual treatment** epochs (See the TEAE period for the 26-week core treatment period in [Section 2.5.4](#)).

- The **posttreatment** epoch is defined as the period of time starting the day after the end of the treatment-emergent adverse event period up to the last protocol-planned visit or the resolution/stabilization of all serious adverse events (SAE), adverse events of special interest (AESI) and events of special interest (EOSI), whichever is later.

The on-study observation period is defined as the time from start of double-blind treatment until the end of the study (defined as the last scheduled visit for those who completed the study and the date collected on e-CRF page “Completion of End of Study/Follow-up” for those who did not complete the study).

The post-study observation period is defined as the time from the day after the end of the study until the resolution/stabilization of all SAE, AESI and EOSI if applicable.

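### The Kaplan-Meier curves for >50% eGFR decline and UACR change should censor at the last laboratory value: EOS, last-contact and Day 182 censoring counts unsampled time as event-free

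*SAP*

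**What the plan says.** SAP 2.4.4.3 plans these curves to Week 26 and to end of study: "A KM plot will be provided for time to first occurrence of >50% decline in eGFR from baseline up to Week 26", and for albuminuria "A KM plot will be provided for time to UACR progression up to Week 26 and the end of study respectively". An improvement curve is added if appropriate.

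The censoring table in SAP 2.5.4 sets the dates for patients without an event:

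- **Week 26 curves.** The earlier of EOS and the date of the laboratory value: "min (EOS, Date of W26/re-allocated W26 eGFR value" and "min (EOS, Date of W26/re-allocated W26 UACR value". If there is no such value, "Day 182 will be used if Date of Week 26 visit (or date of W26/re-allocated W26) is not available".
- **End-of-study curves.** EOS for both rows. If EOS is missing, "Last contact date will be used if date of EOS is not available".

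SAP 2.1.4 makes EOS a study-status date: "defined as the last scheduled visit for those who completed the study", and an e-CRF date for the others. It is not tied to a sample. Protocol 6.1.2 allows follow-up without samples: "If a patient does not agree to site visits, he/she will be contacted by telephone to inquire about their safety status". SAP 2.5.4 also keeps local laboratory results out of the efficacy analyses, so tests done elsewhere cannot fill the gap.

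**The concern.** A >50% fall in eGFR needs a creatinine result, and a change of albuminuria category needs a urine sample. After the last sample, a patient cannot have either event in the data. Under the EOS or last-contact rule that patient still stays in the risk set, so each later Kaplan-Meier step has too large a denominator and the curve sits too low. This holds for UACR improvement as much as for progression.

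The SAP is not consistent on this. Its Week 26 column already ties these rows to the date of a laboratory value; the end-of-study column does not. Under the default in SAP 2.5.3, by-visit percentages leave out patients with missing data, while the curves count the same patients as event-free.

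All patients have stage 4 kidney disease and progression is a stated objective, so readers will look at these plots.

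**Working it through.** The plan states no figure for these curves, so there is none to reproduce. The check compares two censoring rules on the plan's own visit grid.

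**Inputs from the documents**

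- eGFR on Days 7, 14, 21, 28, 56, 84, 126, 182, 273, 364 and 392 (flow chart; chemistry is also drawn at Visit 14).
- UACR on Days 14, 28, 84, 182 and 364 (overnight urine at Weeks 2, 4, 12, 26 and 52).

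**Assumptions, not in the documents**

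- True 52-week incidence p of 5%, 10% or 20%, with constant hazard −ln(1−p)/364 per day.
- A share m of 0%, 10%, 20% or 30% stops giving samples at a time uniform over Days 0-364 but stays in the study to Day 392.
- Hazard in those patients equal to, or twice, that of the others.

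**Step 1: approximate formula.** An event in the interval ending at visit day v is missed if sampling stopped before v, which has probability v/364 in an unsampled patient. Treating event times as uniform over the year, the share of their events missed is q = Σ(interval width × v)/364².

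- eGFR: q = 77,861/132,496 = 0.588
- UACR: q = 89,376/132,496 = 0.675

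The relative shortfall under EOS censoring is about m × q. For m = 10%, 20% and 30% this gives 5.9%, 11.8% and 17.6% for eGFR, and 6.7%, 13.5% and 20.2% for UACR.

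**Step 2: simulation.** 200,000 patients per setting, events dated at the first visit on or after onset, missingness unrelated to risk, p = 10%. Each cell is SAP rule vs last-value rule.

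| Unsampled | eGFR, Week 52 | UACR, Week 52 | eGFR, Week 26 |
|---|---|---|---|
| 0% | 9.9% vs 9.9% | 9.9% vs 9.9% | 5.1% vs 5.1% |
| 10% | 9.5% vs 10.0% | 9.4% vs 10.1% | 5.0% vs 5.1% |
| 20% | 8.9% vs 10.0% | 8.6% vs 9.9% | 4.8% vs 5.1% |
| 30% | 8.2% vs 10.0% | 7.9% vs 9.8% | 4.7% vs 5.1% |

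Across p = 5% to 20%, the Week 52 relative shortfall is about 5-8%, 11-14% and 16-20% for 10%, 20% and 30% unsampled, in line with Step 1. In absolute terms it is about 0.3 to 4 percentage points. The largest Week 26 gap is 10.5% vs 9.4% = 1.1 points (UACR, p = 20%, 30% unsampled).

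**Step 3: informative loss.** With 20% unsampled at twice the hazard, a true eGFR incidence of 11.8% reads 9.7% under the SAP rule and about 10.8% under the last-value rule. The shortfall falls from 2.1 to 1.0 points but does not vanish.

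**The case against.** Much of the plan is already sound here:

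- On the Week 26 curves, a patient with a Week 26 or re-allocated value (window Days 154-227) is censored at that value's date. Day 182 is only a fallback, and EOS still caps it, so an early leaver is censored on leaving.
- A patient with no Week 26 value but an event-free Week 39 value is not unmeasured in the sense that matters.
- Completers have chemistry at Week 56, so their EOS is an eGFR date. The four weeks from the last UACR at Week 52 to EOS change nothing, because no UACR event can be detected then.
- The endpoints are descriptive and outside the testing hierarchy. By-visit counts, renal events of special interest and laboratory abnormality summaries do not use this table.

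All of this stands. It confines the problem mainly to the end-of-study curves and to patients who remain without samples.

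A reader might go further and infer that renal progression will be understated, or that an arm will look safer for the kidney because it was measured less. The documents support neither. They give no rate of unsampled patients and nothing on differences by arm. Patients whose drug is stopped for renal deterioration are asked to keep attending all visits, and telephone contact is a fallback. As an illustration only: with p = 20% and 30% against 10% unsampled, identical arms would differ by 18.8 − 16.6 = 2.2 points (eGFR) or 18.7 − 16.0 = 2.7 points (UACR). The standard error of an arm difference with 92 per arm is √(2 × 0.2 × 0.8/92) = 5.9 points.

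**Conclusion.** The point holds as a conditional one. Where patients stay in the study without central laboratory samples, the end-of-study curves, and to a small degree the Week 26 curves, count unmeasured time as event-free and read too low. That applies to >50% eGFR decline, UACR progression and UACR improvement alike. The figures rest on assumed incidence, an assumed unsampled share, uniform timing of loss and, for the main results, loss unrelated to risk. If nobody is followed without samples, the two rules agree exactly. A distortion between arms would need unequal sampling by arm, which is possible but undocumented. No formal test or primary conclusion is touched. The correction is still worth making, because the present rule can only lower these curves.

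**What to change.** In the SAP 2.5.4 censoring table, for *Time to eGFR decrease* and *Time to UACR progression/improvement*:

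1. Censor at the date of the last non-missing eGFR (or UACR) value on or before the Week 26 cut or end of study, as the curve requires. Patients with no post-baseline value are censored at Day 1.
2. Remove the Day 182, EOS and last-contact defaults for these two rows.
3. Keep EOS for the dialysis and transplant components of ESRD, which can be learned without a sample.
4. State that last-value censoring assumes non-informative loss of sampling. Add a simple sensitivity analysis, for example a doubled hazard after the last sample, and report by arm how many patients have no value at the cut.

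The cost is a few table cells, one note and one short sensitivity analysis. No new data are needed.
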